9.2.1. Multiplicity

No multiplicity adjustment will be performed as only seroconversion and seroprotection rates, and the 95 % CI will be reported.

9.2.2. Methodology for computing CI

9.2.2.1. 95% CIs

The 95% CI for GMTs will be obtained within each group separately. The 95% CI for the mean of log-transformed titer/concentration will be first obtained assuming that log-transformed concentrations/titers are normally distributed with an unknown variance. The 95% CI for GMTs will be then obtained by exponential-transformation (anti-log with power 10) of the 95% CI for the mean of log-transformed titers.

SAS® Code for comparing GMTs:

```
PROC MIXED DATA=<Data>; * specify and sub-select data set as applicable;
    *BY Agegrp; * as applicable;
CLASS trtpn; * other factors may be added, if applicable;
MODEL AVAL = trtpn; * AVAL=logtiter
```

```
* add factors and options (e.g. ALPHA=.. Solutions) as applicable;
  LSMEANS trtpn / CL ALPHA=0.05 STDERR; * modify/adapt as applicable
  Ods output LSMEANS = outmix;
RUN;
QUIT;
Data _outmix;
Set outmix;
   GMT= 10**(Estimate);
   GMT LCL = 10**(Lower);
   GMT UCL = 10**(Upper);
RUN:
SAS® Code for comparing GMFR:
PROC MIXED DATA=<Data> (analysis dataset);
      class trtpn;
      model diff= trtpn Base; * diff = log10Day21 - log10Day0. Base=log10Day0
      Lsmeans trtpn/cl alpha=0.05;
      Ods output LSMEANS = outmix;
run;
Quit;
Data outmix;
Set outmix;
   GMFR = 10**(Estimate);
   GMFR LCL = 10**(Lower);
   GMFR_UCL = 10**(Upper);
Run;
```

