12.6.1 Analysis of Secondary Endpoints

The secondary immunogenicity endpoints are defined in Section 10.4.2.1.

The following analyses for the HI assay (homologous strains) will be performed on the immunogenicity PP:

- GMT (Day 21): The point estimates and the corresponding two sided 95 % CI by treatment group and strain will be calculated as the antilog of the mean and 95 % CI of log transformed titer values;
- SC rate (Day 0 and Day 21): The point estimates and the corresponding two-sided 95 % CI for subjects achieving SC by treatment group and strain will be calculated to determine whether the lower bound of the CI will meet or exceed 30 %;
- SP rate (Day 21): The point estimates and the corresponding two-sided 95 % CI for subjects achieving SP by treatment group and strain will be calculated to determine whether the lower bound of the CI will meet or exceed 60 %.

The analyses for the MN and SRH assays (homologous strains) will be performed on the immunogenicity PP. The GMT, GMFR, and SC rate of the MN antibody assay and the GMA, GMFR, SC rate, and SP rate for the SRH antibody assay will be compared between the treatment groups using descriptive statistics and 95 % CI. For SC rate and SP rate, Fisher's exact tests or chi square tests will be used. GMT and GMFR for MN and GMA and GMFR for SRH will be compared using appropriate analysis of variance models.

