6.3.5. Immunogenicity

Values below the HI antibody responses below the lower limit of quantification (Below limit of Quantification (BLQ)<10, recorded as "< 10") will be attributed a value of 5. All BLQ responses for the SRH antibody will be attributed a value of 2 mm².

For HI assay:

SC rate is defined as the proportion of subjects in a given treatment group with either $a \ge 4$ -fold increase in reciprocal HI titers between Day 0 and Day 21 or a rise of undetectable HI titer (i.e. < 10) pre-vaccination (Day 0) to an HI titer of ≥ 40 on Day 21.

SP rate is defined as the proportion of subjects in a given treatment group attaining a reciprocal HI titer of ≥ 40 on Day 21 (the percentage of vaccine recipients with a serum HI titer of at least 1:40 following vaccination).

For MN assay:

SC rate is defined as the proportion of subjects in a given treatment group with either $a \ge 4$ -fold increase in reciprocal MN titers between Day 0 and Day 21 or a rise of undetectable MN titer (i.e. 7.1) pre-vaccination (Day 0) to an MN titer of ≥ 28.3 at Day 21 post-vaccination.

For SRH assay:

SC rate is defined as the proportion of subjects in a given treatment group showing at least 50 % increase in GMA between Days 0 and 21.

SP rate is defined as the proportion of subjects in a given treatment group attaining an area $\geq 25 \text{ mm}^2$ following vaccination (Day 21).

GMT calculation:

The GMT calculations are performed by taking the anti-log of the mean of the log titer transformations. The back-transformation for mean GMT will be calculated with two-sided, 95% confidence limits, based on the Analysis of Variance (ANOVA) model.

GMFR calculation:

The GMFR will be derived by using Analysis of Covariance (ANCOVA) to model the difference in the log of the titer values between Day 21 and Day 0, with treatment group as main effect and baseline titer as covariate. The GMFR will be compared between the treatment groups. The comparisons between the treatment groups will be performed using two-sided, 95% confidence, based on the least-squares mean differences from the ANCOVA model.

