9.2. Analysis of Secondary Endpoints

The secondary immunogenicity endpoints are defined in Section 4.3.1.

HI antibody titers will be analyzed and evaluated as follows:

- GMTs of HI antibody: The point estimates and the corresponding two sided 95 % CI by treatment group and strain will be calculated as the antilog of the mean and 95 % CI of log transformed titer values on Days 0 and 21;
- SC rate: The point estimates and the corresponding two-sided 95 % CI for subjects achieving SC by treatment group and strain will be calculated and reported;
- SP rate: The point estimates and the corresponding two-sided 95 % CI for subjects achieving SP by treatment group and strain will be calculated and reported.
- GMFR: the geometric mean of the ratio of GMTs (Day 21/Day 0).

MN antibody response against the homologous influenza strains on Days 0 and 21 will be analyzed as follows:

- GMTs of MN antibody on Days 0 and 21(as defined above for HI);
- SC rate: the proportion of subjects in a given treatment group with either a ≥ 4-fold increase in reciprocal MN titers between Day 0 and Day 21 or a rise of undetectable MN titer (i.e. 7.1) pre-vaccination (Day 0) to an MN titer of ≥ 28.3 at Day 21 post-vaccination.
- GMFR: the geometric mean of the ratio of GMTs (Day 21/Day 0).

SRH antibody response against the homologous influenza strains will be analyzed as follows:

- GMAs of SRH antibody on Days 0 and 21;
- SC rate: proportion of subjects in a given treatment group showing at least 50% increase in GMA between Days 0 and 21;
- SP rate: the proportion of subjects in a given treatment group attaining an area ≥ 25 mm² following vaccination (Day 21);
- GMFR: the geometric mean of the ratio of GMAs (Day 21/Day 0).

The GMFR will be derived by using ANCOVA to model the difference in the log of the titer values between Day 21 and Day 0, with treatment group as main effect and baseline titer as covariate

The GMTs, GMFRs, SP and SC rates of the HI antibody assay, the GMTs, GMFRs and SC rates of and the MN antibody assay, and the GMAs, GMFRs, SC rates, and SP rates for the SRH antibody assay will be compared between the treatment groups using descriptive statistics and 95% CI.

For SC rate and SP rate, Fisher's exact tests will be used. GMT for HI, MN and GMA for SRH will be compared between treatment groups using the ANOVA model. GMFR for HI, MN and SRH will be compared using the ANCOVA model.

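### The SAP describes each arm's GMT confidence interval as obtained separately by arm, but its code and section 6.3.5 take the limits from one model with a shared residual variance

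*SAP*

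**What the plan says.** Five places bear on how the per-arm GMT limits are calculated.

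- **SAP 9.2.2.1, text.** The rule is: "The 95% CI for GMTs will be obtained within each group separately". The next sentence derives the interval for the mean log titre "assuming that log-transformed concentrations/titers are normally distributed with an unknown variance" and then back-transforms it.
- **SAP 9.2.2.1, code.** The block directly below fits a single `PROC MIXED` with "MODEL AVAL = trtpn". It has no `BY trtpn` and no `REPEATED / GROUP=`. The lower and upper limits from `LSMEANS` are raised to the power of 10 and stored as the GMT limits.
- **SAP 6.3.5.** The back-transformed GMT is reported with "95% confidence limits, based on the Analysis of Variance (ANOVA) model".
- **SAP 9.2.** For HI, the estimates and intervals "by treatment group and strain will be calculated as the antilog of the mean and 95 % CI of log transformed titer values". Nothing is said about which variance is used.
- **Protocol 12.6.1.** The HI GMT and its interval are "the antilog of the mean and 95 % CI of log transformed titer values", again with no statement about the variance.

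SAP section 12 lists changes from the protocol and settles the MN seroconversion cut-off, but it does not address this point. The seroconversion and seroprotection code in SAP 9.2.2.2, by contrast, is run within each arm through a `BY` statement that includes `trtpn`.

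**The concern.** One reported quantity, the 95% interval around an arm's GMT, is governed by two rules. Read naturally, the text of 9.2.2.1 gives a one-sample t interval from that arm's own SD. The code, and a standard reading of ANOVA in 6.3.5, give an interval from an SD pooled over both arms. The point estimate is the same under either rule; the width is not, unless the two SDs happen to agree.

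The arms receive different products: a plant-derived VLP vaccine at 30 µg/strain and an egg-derived split-virion vaccine at 15 µg/strain. Equal spread of log titres is therefore an assumption. If it fails, the pooled rule overstates uncertainty in one arm and understates it in the other. What is at stake is the stated coverage of the single-arm GMT intervals in the 420-subject subset, and whether two programmers following the SAP would produce the same table.

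**Working it through.** **Inputs from the documents.** Two-sided 95% intervals (SAP 6.1); 210 subjects per arm in the immunogenicity subset (SAP 4.3.1); the model and `LSMEANS` code in SAP 9.2.2.1. The documents give no GMT interval width or titre SD, so there is no plan figure to reproduce.

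**Assumed input.** Log10-titre SD of 0.5 in one arm and 0.5 × r in the other, with r from 1.0 to 1.5. With equal arms, the relative widths and the coverage depend only on r.

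**Formulas**, for arm i with n per arm:

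- Text rule: half-width = t(0.975, n − 1) × s_i / √n.
- Code rule: half-width = t(0.975, 2n − 2) × s_p / √n, with s_p² = (s_1² + s_2²)/2.

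**Check that the coded model behaves this way.** A one-way fit to one simulated data set (n = 210 per arm, sample SDs 0.517 and 0.729) gave the same standard error, 0.0436, for both arm means. By hand, s_p = √((0.517² + 0.729²)/2) = 0.632, and 0.632/√210 = 0.0436. The arms' own standard errors are 0.0357 and 0.0503.

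**Width by hand at r = 1.25.** s_p/s_low = √((1 + 1.25²)/2) = 1.132, and s_p/s_high = 1.132/1.25 = 0.906. The ratio of the two t quantiles is 0.997, giving 1.129 and 0.903. Large-sample coverage is 2Φ(1.96 × 1.132) − 1 = 97.3% and 2Φ(1.96 × 0.906) − 1 = 92.4%.

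**Results at 210 per arm** (coverage from 200,000 simulations per setting):

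| SD ratio | Coded / own half-width, low-SD arm | Coded / own half-width, high-SD arm | Coverage, low-SD arm | Coverage, high-SD arm |
|---|---|---|---|---|
| 1.0 | 0.997 | 0.997 | 95.0% | 95.0% |
| 1.1 | 1.048 | 0.953 | 96.0% | 94.0% |
| 1.25 | 1.129 | 0.903 | 97.3% | 92.3% |
| 1.5 | 1.271 | 0.847 | 98.8% | 90.3% |

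The own-variance interval, checked in the high-SD arm, covers 94.9 to 95.1% at each of these ratios. On the titre scale at r = 1.5 (SDs 0.5 and 0.75), the coded interval is the GMT times or divided by 1.22 in both arms, against 1.17 and 1.27 with own variances.

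**Dependence on n.** s_p/s_i does not involve n. At 70 per arm, about the size of the older stratum under the 2:1 age split (210/3), coverage is 97.3/92.5% at r = 1.25 and 98.7/90.3% at r = 1.5. With SDs of 0.5 and 0.6, simulated coverage in the high-SD arm is 92.8%, 92.5% and 92.8% at 70, 210 and 2,100 per arm.

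**Between-arm comparison.** With equal n, the pooled standard error of the difference is √(2 s_p²/n) = √((s_1² + s_2²)/n), which is exactly the separate-variance standard error. Only the degrees of freedom differ. At r = 1.5 these are 418 against (1 + 2.25)² × 209 / (1 + 2.25²) ≈ 364, a negligible change.

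**The case against.** The case for leaving this alone has several parts.

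- **Pooled limits are legitimate.** Least-squares-mean limits with a common variance are a standard choice and are exact when the variances are equal. The code and 6.3.5 agree with each other. This stands: the fault is that the SAP states two rules, not that pooling is inadmissible.
- **The other sections do not settle it.** A reader might infer that SAP 9.2 and protocol 12.6.1 also require arm-specific variances. They do not: neither mentions variance, and a pooled interval reported by arm would fit their wording. The own-variance rule rests on the text of 9.2.2.1 alone.
- **The code is a template for comparison.** It is headed as code for comparing GMTs, carries comments inviting adaptation, and lacks `BY` processing for strain or visit. That stands as far as it goes. But it requests no difference between arms, outputs only per-arm GMTs and limits, and sits under the section on computing intervals. The heading does not remove the conflict, and leaving adaptation to the programmer leaves the choice of rule open.
- **No SD is documented.** This also stands. Different products make unequal spread possible, not established; at a ratio of 1.1 the shift in coverage is about one percentage point in each arm.
- **Nothing is decided on these limits.** GMT has no success threshold. The 30% and 60% criteria in protocol 12.6.1 apply to seroconversion and seroprotection rates, whose exact intervals are already computed by arm.

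**Conclusion.** The inconsistency is real but minor. The SAP's text and its code prescribe different variances for the per-arm GMT interval, 6.3.5 sides with the code, and nothing in the SAP reconciles them. That 6.3.5 means a common variance is itself inferred from the usual meaning of ANOVA and the default of the coded model.

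The consequence is conditional. With equal SDs the two rules agree to within 0.3% in width. At an assumed ratio of 1.25, coverage is about 97/92% (low-SD / high-SD arm), and at 1.5 about 99/90%; a larger sample does not correct this. The figures assume normal log titres and equal arms, and the SD ratios are illustrations.

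Two stronger readings are not supported. A reader might infer that the planned GMT intervals are wrong; without titre SDs that cannot be said, only that their coverage is not assured. A reader might also infer that the vaccine comparison is compromised. Under 1:1 allocation it is essentially unchanged, as are the point estimates and the primary efficacy analysis. Only the descriptive single-arm intervals in the 420-subject subset are affected.

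**What to change.** Compute the displayed GMT limits by arm, as the text of SAP 9.2.2.1 describes. Either run the estimation with `BY trtpn`, or add `REPEATED / GROUP=trtpn` with Satterthwaite degrees of freedom to the existing model. Treat the SRH GMA limits in the same way for consistency, although the wording on separate intervals names only GMTs. Amend SAP 6.3.5 so that the per-arm limits come from each arm's own variance. The ANOVA model can stay for the between-arm comparison.

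The cost is about one line of code and one sentence, with essentially no loss of precision at 210 per arm even if the SDs are equal. If the sponsor does intend a pooled variance, rewording 9.2.2.1 to say so would also remove the contradiction, but coverage would then still depend on equal SDs. The by-arm interval is therefore the better choice.

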9.2.2.2. Exact 95% CIs

The exact 95% CIs (Clopper-Pearson method) will be used for proportion of SC and SP subjects within a group.

SAS® Code for SC and SP (Exact 95% CIs):

```
PROC FREQ data=<Data>;
    BY ANTIGEN trtpn;
    TABLE SC/out=CNT binomial; *SC or SP
    EXACT binomial;
    ODS OUTPUT binomialprop=bin (where=(name1 in ('XL_BIN', 'XU_BIN')));
run;
```

9.3. Analysis of Exploratory Endpoint

The exploratory immunogenicity endpoint is defined in Section 4.3.2.

The CMI response induced by the Quadrivalent VLP Influenza Vaccine against homologous strains on Day 21 (in the subset of 420 subjects) will be compared between the treatment groups using non-parametric (Wilcoxon) models for each strain and parameter by age group and overall.

For CMI response CD4+ cells results will be presented along with available subjects (n), in terms of mean, median, SD, min and max. For the p-value calculation between the treatment groups for individual parameters, Wilcoxon rank-sum test will be used for Day 21, whereas the p-value will be calculated using Wilcoxon signed rank test for the difference between Day 0 and Day 21 values.

In addition, an individual listing will be provided to include CMI CD4+ cells response for each parameter with % response CD4+cells by subject and age stratum. The responses of each parameter will be illustrated using plots such as box plots by treatment group with parameters as X-axis and percentage of CD4+ T cells (%) as Y-axis.

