12.6.2 Analysis of Exploratory Endpoint

The exploratory immunogenicity endpoint is defined in Section 10.4.2.2.

The CMI response will be compared between the treatment groups using appropriate non-parametric (Wilcoxon) models. Additional details will be provided in the SAP.

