3.3. Exploratory Objectives

Efficacy:

- To evaluate the efficacy, relative to an active comparator, of a single 30 μg/strain dose
 of the Quadrivalent VLP Influenza Vaccine, against protocol-defined respiratory illness
 due to mismatched influenza strains (sequential RT-PCR & serotyping);
- To determine the efficacy, relative to an active comparator, of a single 30 μg/strain dose
 of the Quadrivalent VLP Influenza Vaccine, as measured by the incidence of subjects
 presenting with symptoms of protocol-defined respiratory illness, regardless of
 laboratory results.
- 3. To evaluate whether or not vaccine efficacy (VE) is maintained (no waning) through time after vaccination for the primary efficacy endpoint, that is, protocol-defined ILI caused by any influenza viral type/subtype.

Safety:

1. To evaluate respiratory illness outcome, occurrences of pneumonia, new onset or exacerbations of cardio-respiratory conditions, and health care utilization of subjects administered the Quadrivalent VLP Influenza Vaccine at a dose of 30 μg/strain relative to subjects administered an active comparator.

Immunogenicity:

[figure not shown]
1. To assess the Cell-Mediated Immune (CMI) response against homologous strains of a single 30 μg/strain dose of Quadrivalent VLP Influenza Vaccine and an active comparator on Days 0 and 21 in a subset of 420 subjects (same subset as the immunogenicity subset; 210 subjects per treatment group).

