¹ Nasopharyngeal (NP) swabs are to be collected for any subject who reports any respiratory illness as per regional specifications: after the start of the local influenza season (subjects in North America and Europe) or for any respiratory illness reported during the surveillance period (i.e. Day 14 onwards; subjects in Asia).

⁴ After vaccination, subjects will be instructed on the diary and memory aid provided for their use for recording reactions, AEs, concomitant medication use, and respiratory illness symptoms. They will be reminded of the reportable respiratory illness symptoms that will trigger the need for NP swabbing, as well as of the overall active and passive surveillance process.

² Swabs are to be collected within 36 hours after reporting of the respiratory illness (preferably within 24 hours) and prior to the use of influenza antiviral treatment medication (e.g. oseltamivir, zanamivir, rapivab). If swabs cannot be collected within 36 hours after reporting of the respiratory symptoms, NP swabs should still be collected if the subject still has at least one respiratory illness symptom.

³ After NP swab collection and until the final 30 (+ 7) day follow-up, the planned active surveillance (phone and text messaging) will continue and will include questions on the respiratory illness progression.

Days after Reporting of Respiratory Illness ¹	0-1.5 Days	0-1.5 Days ²	Monitoring ³	30 (+ 7) Days ⁴
Contact Type	Phone	Visit	Phone / Text Messaging	Phone

⁴ The seven-day window allows provision to complete the telephone call. Information from more than 30 days from respiratory illness onset does not need to be collected.

Table 3 Estimated Blood Volume Drawn

Type of Sample	Volume per Sample (mL)	Number of Samples per Subject	Total Volume of Blood per Subject (mL)
CMI response	50	2*	100*
HI, MN, and SRH titers	10	2*	20*

^{*} Day 0 and Day 21 samples to be collected for a pre-defined subset of 420 subjects.

⁵ During collection of information on respiratory illness symptoms, the presence or absence of concurrent systemic symptoms (i.e. fever, feverishness [feeling of warmth], chills [shivering], tiredness [fatigue], headache, myalgia [muscle aches], nausea, vomiting, or diarrhea) will also be collected.

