4.3.2. Exploratory Endpoint

CMI response induced by the Quadrivalent VLP Influenza Vaccine against homologous strains on Day 21 (subset of 420 subjects), as measured by the number of CD4+ T cells expressing each of three functional markers: interferon gamma (IFN- γ), interleukin-2 (IL-2), and tumor necrosis factor alpha (TNF- α), as well the number of cells producing at least one of these cytokines and the number of cells producing two or more of these cytokines.

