9. ANALYSIS OF IMMUNOGENICITY

9.1. Immunogenicity Evaluation

Immunogenicity will be evaluated by the humoral immune response (HI, MN, and SRH assays) and the CMI response induced in subjects on Days 0 and 21 in a subset of 420 subjects (210 from each treatment group) from selected sites. The North American sites selected for this subset of 420 subjects will be pre-defined prior to study start and will target providing a representative age distribution. The number of subjects in each age group (65 to 74 years of age and 75 years of age and older) included in the immunogenicity analyses will be similar in proportion to that of the overall study.

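### The between-arm CMI test in SAP 9.3 leaves out the planned Day 0 sample, and the one test that uses Day 0 cannot compare the arms

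*SAP*

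**What the plan says.** Protocol 12.6.2 sets the general rule and leaves the details to the SAP: "The CMI response will be compared between the treatment groups using appropriate non-parametric (Wilcoxon) models".

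SAP 9.3 fills in those details in one sentence with two halves. The first half gives the between-arm test: "Wilcoxon rank-sum test will be used for Day 21". The second half brings in Day 0: "the p-value will be calculated using Wilcoxon signed rank test for the difference between Day 0 and Day 21 values". The sentence opens by referring to p-values between the arms and nowhere says that its second half is a within-arm analysis.

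The SAP is not uniform about the time points. The objective in SAP 3.3 covers both: "comparator on Days 0 and 21 in a subset of 420 subjects". The endpoint in SAP 4.3.2 names only one: "CMI response induced by the Quadrivalent VLP Influenza Vaccine against homologous strains on Day 21 (subset of 420 subjects". The Day 0 blood is planned either way. Table 3 in SAP 3.9 notes: "Day 0 and Day 21 samples to be collected for a pre-defined subset of 420 subjects".

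For the antibody assays the SAP does use baseline. SAP 6.3.5 and 9.2 model the HI, MN and SRH fold rise by ANCOVA with the Day 0 value as covariate. SAP 9.3 has no counterpart for CMI.

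**The concern.** There are two difficulties.

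The first is precision. If Day 0 and Day 21 values are correlated, part of the spread in Day 21 values reflects where each subject started. A test on Day 21 alone treats that spread as noise. Each subject in the subset gives 50 mL of blood for CMI at Day 0, and that sample adds nothing to the comparison of arms.

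The second is interpretation. A signed rank test takes paired differences from one sample and asks whether they centre on zero. It cannot compare two independent arms. As worded, the SAP could leave a reader with a significant change in one arm, a non-significant change in the other, and the impression that the arms have been compared.

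A between-arm CMI result will be looked for. Protocol 1.4 rests its hope of better protection in the elderly on the combined humoral and cellular response. Protocol 1.3.2.2 reports a lesser response with an active comparator against H1N1 and H3N2 in earlier studies, with similar responses against the B strains.

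**Working it through.** **Is there a figure to reproduce?** No. Neither document gives a power, effect size, SD or Day 0 to Day 21 correlation for CMI. The size of the loss therefore has to be shown over a range.

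**Inputs from the documents.** 210 subjects per arm (SAP 9.1: "in a subset of 420 subjects (210 from each treatment group) from selected sites"); two-sided alpha of 0.05 (SAP 6.1).

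**Assumed inputs.** A true between-arm difference of 0.25 SD of the Day 21 value, and a correlation ρ of 0, 0.3, 0.5 or 0.7.

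**Formulas.** Baseline adjustment multiplies the variance of the between-arm difference by 1 − ρ². In SD units, with n per arm:

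- standard error = √((1 − ρ²) × 2/n)
- power = Φ(0.25 / standard error − 1.96)
- difference detectable at 80% power = (1.96 + 0.842) × standard error
- equivalent unadjusted sample per arm = n / (1 − ρ²)

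**Unadjusted case.** √(2/210) = 0.0976; 0.25/0.0976 = 2.562; 2.562 − 1.96 = 0.602; Φ(0.602) = 72.6%. This does not depend on ρ.

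**Adjusted cases, 210 per arm.** The last two columns come from a simulation of the rank tests themselves (log-normal data, 4,000 runs per setting).

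| ρ | Variance removed | Equivalent n per arm | Power, adjusted | Detectable difference (SD) | Simulated Day 21 rank-sum | Simulated rank ANCOVA |
|---|---|---|---|---|---|---|
| 0 | 0% | 210 | 72.6% | 0.273 | 70.3% | 70.4% |
| 0.3 | 9% | 231 | 76.6% | 0.261 | 70.3% | 74.2% |
| 0.5 | 25% | 280 | 84.1% | 0.237 | 71.2% | 81.1% |
| 0.7 | 49% | 412 | 94.8% | 0.195 | 72.0% | 93.0% |

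With no true difference, both rank tests rejected in 4.6% to 5.2% of runs, so both hold their level.

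**Fewer subjects.** If the trial's 10% dropout assumption is borrowed for the subset, 210 × 0.9 = 189 per arm. Unadjusted power is then 68.1%, against 72.2%, 80.1% and 92.6% at ρ of 0.3, 0.5 and 0.7.

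**Missing Day 0 results.** Suppose a fraction m of subjects with a Day 21 result has no valid Day 0 result. The adjusted analysis still gains when n(1 − m)/(1 − ρ²) exceeds n, that is when m < ρ². The break-even points are 9%, 25% and 49% at ρ of 0.3, 0.5 and 0.7.

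**Would a rank-sum test on the change do as well?** Not reliably. In the same simulation its power was 53%, 66% and 86% at ρ of 0.3, 0.5 and 0.7. It falls below the Day 21 test at the two lower values.

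**Do separate within-arm tests fill the gap?** A second simulation (3,000 runs per setting, 210 per arm, ρ = 0.5) gave both arms the same true response. With responses of 0.10, 0.15 and 0.20 SD, exactly one arm was significant in 42%, 49% and 33% of trials.

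**The case against.** The strongest defence is that SAP 9.3 does what the protocol asks. The endpoint is CMI at Day 21, Protocol 12.6.2 calls for a Wilcoxon comparison, and the rank-sum test supplies one that is valid. CMI is exploratory, with no power target or success criterion, and rank ANCOVA is one acceptable choice among several. All of this stands. It makes the point an improvement to the plan and not the correction of an invalid test.

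The gain also rests on an unknown correlation and may be small. That stands too: at ρ = 0.3 it is four percentage points.

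Nor is full Day 0 data assured. Samples are planned for 420 subjects, but Protocol 16.1 says that not all may be analysed. The immunogenicity per protocol set (SAP 5.4) requires a Day 21 sample without naming Day 0, and SAP 6.4 excludes subjects with missing values. This is a fair limit, and the break-even fractions show how much missing Day 0 data the adjusted analysis can bear.

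Finally, the SAP does not say that significance in one arm will be set against non-significance in the other. That is so. The wording leaves the misreading open but does not commit to it.

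A reader might also infer that SAP 9.2 has the same fault, because Day 21 GMT and GMA "will be compared between treatment groups using the ANOVA model", with no baseline term in the specified model. The documents do not support carrying the point over. The GMFR model regresses log Day 21 minus log Day 0 on treatment and log Day 0. Moving log Day 0 to the right-hand side changes only its own coefficient, so the treatment coefficient and its standard error are those of a baseline-adjusted Day 21 analysis. The adjusted contrast for those assays is already planned.

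**Conclusion.** The point holds as a loss of precision and interpretability in an exploratory analysis. SAP 9.3 compares the arms on Day 21 CMI only, and its one use of Day 0 cannot compare arms despite the way the sentence opens.

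For an assumed 0.25 SD difference with 210 per arm, power is about 73% as planned. With adjustment it is about 77%, 84% and 95% at assumed correlations of 0.3, 0.5 and 0.7, and there is no gain at zero. The 210 per arm also supposes that all planned samples yield results.

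Two stronger readings should be resisted. One is that the Day 21 test is biased: under randomisation it is not, and its simulated error rate was about 5%. The other is that the gain must be large because influenza-specific T cells are already present before vaccination in this age group. The documents report no Day 0 CMI levels and no correlation, so they cannot support that.

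**What to change.** In SAP 9.3:

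- Make the main between-arm CMI comparison a rank ANCOVA, with Day 21 ranks adjusted for Day 0 ranks and stratified by age group, in subjects with both samples. The subset comes only from North American sites, so age is the one randomisation stratum that varies within it.
- Keep the Day 21 rank-sum test as supportive. This retains the Wilcoxon comparison named in the protocol and covers subjects without a valid Day 0 result.
- Reword the signed rank sentence so that those tests are labelled within-arm and descriptive.
- Record the change in SAP section 12 before unblinding.

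SAP 9.2 needs no change on this point.

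The cost is a few sentences and a few lines of code, with no new samples. The one price is that subjects without a valid Day 0 result drop out of the main comparison, which is why the rank-sum test stays.
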